2	3/16/2022	Increased compensation to \$100 split into two payments of \$25 and \$75. (Section 15.4) Clarified exclusion criteria: no contraceptive use, no recent (within 12 mo) or current eating disorder (Section 12.2) Expanded on protocol justification (Section 3.3) Clarified running time of protocol (Section 8.1)	Yes
3	3/29/2022	Added pregnancy test after the 3-week washout period on day 1 of the second experimental condition (Sections 8.1, 8.2, 12.3, 17.4)	Yes
4	5/20/2022	Protocol for impact loading exercise sessions modified slightly to include recovery period (Section 8.2) Additional assays (leptin, cortisol, ferritin, 25(OH)D, Nesfatin-1) (Section 4.1 and Table 1 in Section 8) Added vitamin D questionnaire at baseline (Section 8.2) Change to weight safety endpoint (Section 4.2 and justification in section 7.2) Change timepoints for running economy Added menstrual cycle question to phone screening form	Yes
5	6/24/2022	Baseline DXA moved from visit 2 to visit 1 (Section 8.2)	Yes

22-168 The Effect of Impact Loading on Bone Biomarkers in Energy-Restricted Female Runners

		Added a mealtime log during the 5-day experimental phases (Section 8.2) Protocol for treadmill run decreased to 65%VO2max (previously 70%VO2max) (Section 8.2)	
6	9/6/2022	Inclusion criteria adjusted to include participants ages 18-35 (previously 18-30) and removed running requirement of 30 miles/week and VO2max criteria (Section 12) Additional iron status markers (TIBC and serum iron) (Section 4.1, Table 1 Section 8) Exclusion criteria: criteria for low BMD adjusted to z-score <-2 (Section 12)	Yes
7	7/10/2023	Inclusion criteria adjusted to include participants with a BMI 18.5-30 (Section 12)	Yes
8	9/8/23	Increase sample size to 20	No

Table of Contents

1.0	Study Summary	5
2.0	Objectives	6
3.0	Background	6
4.0	Study Endpoints	10
5.0	Study Design and Statistical Analysis Plan	11
6.0	Setting	12
7.0	Study Intervention(s)/Investigational Agent(s)	12
8.0	Procedures Involved	14
9.0	Data and Specimen Long Term Storage and Use	24
10.0	Sharing of Results with Subjects	26
11.0	Study Timelines	27
12.0	Inclusion and Exclusion Criteria	27
13.0	Vulnerable Populations	29
14.0	Number of Subjects	30
15.0	Recruitment Methods	31
16.0	Withdrawal of Subjects	32
17.0	Risks to Subjects	33
18.0	Potential Benefits to Subjects	36
19.0	Data Management and Confidentiality	37
20.0	Provisions to Protect the Privacy Interests of Subjects	39
21.0	Provisions to Monitor the Data to Ensure the Safety of Subjects	40

1.0 Study Summary

Study Title	The Effect of Impact Loading on Bone Biomarkers in Energy-Restricted Female Runners
Study Design	Randomized Cross-Over Intervention Study
Primary Objective	Determine the effect of short-term, high-impact loading on biomarkers of bone remodeling in trained, female long-distance runners in the presence of low energy availability.
Secondary Objective(s)	Exploratory Aim: Examine the relationship between undercarboxylated osteocalcin and impact loading on glucose metabolism during acute low energy availability.
Study Population	Eumenorrheic, female long-distance runners who do not have existing low energy availability.
Sample Size	20
Research Intervention(s)/Investigational Agent(s)	Research volunteers will undergo two experimental conditions of low energy availability in a randomized order: Low energy availability with daily running only (RUN) and low energy availability with daily running and impact loading (RUN+IL). Each 5-day experimental condition will be initiated in the follicular phase and separated by a washout period of one menstrual cycle (approximately 24 days).
Study Duration for Individual Participants	19 days of intervention and study visits including one screening visit, one baseline testing visit, 3 days of tracking normal diet and exercise, and two experimental conditions of 7 days separated by a 3-week washout period of normal diet and exercise
Acronyms and Definitions	ACSM, American College of Sports Medicine; BMD, bone mineral density; CBC, complete blood count; CGM, continuous glucose monitoring; CTX, C-terminal telopeptide of type 1 collagen; DXA, Dual-Energy X-ray Absorptiometry; HIP Laboratory, Human Integrated Physiology Laboratory; LEA, low energy availability; NEM Laboratory, Nutrition and Exercise Metabolism Laboratory; P1NP, N-terminal propeptide of type 1 procollagen; Trap5b, tartrate-resistant acid phosphatase; TSH, thyroid-stimulating hormone; unOC, undercarboxylated osteocalcin; VO ₂ max, maximal oxygen uptake during exercise, also known as aerobic capacity;

2.0 Objectives

2.1 *Describe the purpose, specific aims, or objectives of this study:*

- 1) Determine the effect of short-term, high-impact loading on biomarkers of bone remodeling in energy-restricted, female long-distance runners.
- 2) Examine the relationship between undercarboxylated osteocalcin and impact loading on glucose metabolism during acute low energy availability.

2.2 *State the hypotheses to be tested:*

The addition of 50 high-intensity impact loading jumping exercises per day to usual run training will result in less suppression of bone formation following 5 days of endurance running in an energy-restricted condition compared to daily running in an energy-restricted state without high-impact loading exercises.

3.0 Background

3.1 *Summarize the relevant prior research on this topic and gaps in current knowledge within the field of study:*

Maintaining adequate energy intake is essential for athletic performance and overall general health. Yet, many athletes experience low energy availability (LEA) by failing to consume enough calories to meet their energy demands. Energy availability is the amount of energy remaining from dietary energy intake (EI) to support general health and bodily functions after accounting for exercise energy expenditure (EEE), and is commonly expressed relative to fat-free mass as kilocalories per kilogram of fat-free mass (FFM) per day (kcal/kgFFM/d). According to the Life History Theory, the human body will adapt to conserve energy under conditions of biological stress, such as energy-restriction and LEA, by downregulating biological processes that are less essential for immediate survival (Shirley, Long et al. 2022). The performance and health consequences of LEA are characterized by the syndrome known as Relative Energy Deficiency in Sport (RED-S) (Mountjoy, Burke et al. 2018). Specific to this proposed study, athletes suffering from RED-S and chronic LEA may experience several inter-related health consequences involving endocrine function, reproduction, and bone metabolism. Previous studies indicate LEA is associated with increased risk for bone stress injuries and low bone mineral density (BMD) (Tenforde, Carlson et al. 2016, Tenforde, Carlson et al. 2018, Gibbsm Battuv et ak, 2014), in addition to suppression of certain bone-regulating hormones including estrogen, insulin, vitamin D, triiodothyronine (T3), and insulin-like growth factor (IGF-1) (McCall, Ackerman 2019).

Previous Studies on LEA and Biomarkers of Bone Metabolism. Biomarkers of bone formation and resorption are often used as surrogate markers for assessing bone metabolism in the short term given that it can take months or even years for changes in bone microarchitecture and BMD to manifest. In a study of 8 male distance runners,

22-168 The Effect of Impact Loading on Bone Biomarkers in Energy-Restricted Female Runners

serum N-terminal pro-peptide of type 1 collagen (P1NP), a marker of bone formation, and IGF-1 decreased by 15% and 17%, respectively, after 3 consecutive days of treadmill running with energy intake restricted to 50% of estimated needs (Zanker and Swaine 2000). In a more recent cross-over design study (Papageorgiou, Elliott-Sale et al. 2017), changes bone biomarkers were measured in 11 women and 11 men in response to 5 days of daily running under optimal EA conditions (45 kcal/kgFFM/d) and 5 days of daily running under low EA conditions (15 kcal/kgFFM/d). In both conditions, participants ran on a treadmill until an energy expenditure of 15 kcal/kgFFM was achieved. Diets provided 60 kcal/kgFFM/d and 30 kcal/kgFFM/d for the optimal and low EA conditions, respectively. In the female participants, P1NP was significantly lower after the low EA condition compared to optimal EA. Additionally, β -carboxyl-terminal cross-linked telopeptide of type 1 procollagen (β -CTX), a marker of bone resorption, increased 19% in response to the low EA condition and this increase was significantly different from the change in β -CTX observed in the optimal EA condition. No significant change in P1NP or β -CTX were observed in men. This suggests women may be more sensitive to the effects of LEA on bone metabolism and, therefore, be at greater risk. In another cross-over design study of 10 female runners, changes in P1NP and β -CTX were measured after completion of three, 3-day experimental conditions: optimal EA (45 kcal/kgFFM/d), LEA achieved through dietary restriction only (15 kcal/kgFFM/d), and LEA achieved through a combination of dietary restriction and daily running (15 kcal/kgFFM/d) (Papageorgiou, Martin et al. 2018). In the combined diet and exercise LEA condition, participants received diets providing 30 kcal/kgFFM/d and expended 15 kcal/kgFFM/d during a treadmill run. This study found P1NP was significantly reduced after 3 days of LEA achieved through diet only, but not after the combined LEA condition with running. These findings suggest the negative effects of LEA on bone metabolism may be counteracted or masked by the osteogenic effects of weight-bearing exercise, such as running. There were no significant changes observed in β -CTX in response to either LEA condition. Based on these short-term studies, it appears suppression of bone formation occurs before measurable increases in bone resorption. Additionally, the severity of bone impairments may depend on the degree of energy restriction given the dose-response relationship observed between LEA and select bone turnover markers in exercising women (Ihle and Loucks 2004).

Benefit of High-Impact Loading on Bone Metabolism. High-impact loading exercises such as jumping, bounding, and plyometric training place a high level of mechanical strain on bone and can elicit osteogenic adaptations (Hutson, O'Donnell et al. 2021). There have been a limited number of studies showing mixed results on the short-term effects of high-impact loading on bone biomarkers (Rantalainen, Heinonen et al. 2009, Rogers, Dawson et al. 2011). Additionally, very few studies have included energy intake assessments and most studies have been conducted in non-athletes. In one study of 26 female non-athletes, markers of bone formation (osteocalcin and bone specific alkaline phosphatase (BAP)) and bone resorption (tartrate-resistant acid phosphatase (TRAP5b) and CTX) were measured in response to either a control condition or jumping intervention (Kishimoto, Lynch et al. 2012). Volunteers in the jump group performed 10 jumping exercise per day at a frequency of 5 times a week for 2 weeks. Bone resorption measured by CTX was lower in the jump group compared to baseline. Additionally, TRAP5b was significantly lower in the jump group compared to the control group,

22-168 The Effect of Impact Loading on Bone Biomarkers in Energy-Restricted Female Runners

however, there was no significant changes in TRAP5b from baseline in either group. Interestingly, the jump intervention significantly lowered BAP, a marker of bone formation. No changes were observed in osteocalcin within or between groups. This study was limited based on lack of energy intake assessment and the potential for inter-subject variability in bone response to jumping exercises. Despite the theoretical basis for high-impact exercise as a countermeasure for bone resorption during LEA, there have been no controlled trials to date that have investigated this theory in energy-restricted athletes.

Undercarboxylated Osteocalcin (unOC) and Glucose Metabolism. This study seeks to contribute to understanding the potential association between osteocalcin in glucose metabolism in humans. Undercarboxylated osteocalcin (unOC) is the active form of osteocalcin and is released in response to osteoclast activity during bone resorption (Moser and van der Eerden 2019). The role of unOC to regulate glucose metabolism in humans is unclear (Lin, Brennan-Speranza et al. 2018). In a cross-sectional study, unOC was found to be associated with insulin secretion and sensitivity in lean male patients ($BMI < 25 \text{ kg/m}^2$) (Fernández-Real, Izquierdo et al. 2009). Subjects in this study were generally healthy and non-athletes. In a meta-analysis of osteocalcin and glucose metabolism, a weak negative correlation ($r=-0.09$, $p<0.5$) was found between unOC and fasting plasma glucose in women (Liu, Guo et al. 2015). However, the association between unOC and glucose metabolism was found to be stronger in men than in women. There is limited data on the effects of LEA on glucose metabolism in athletes without diabetes. One study of 7 male long-distance runners found muscle glycogen was reduced by approximately 30% after 3 days of endurance training under energy-restricted conditions ($EA = 18.9 \pm 1.9 \text{ kcal/kgFFM/d}$) (Kojima, Ishibashi et al. 2020). No studies to date have investigated the relationship between undercarboxylated osteocalcin and glucose metabolism in energy-restricted athletes.

3.2 *Describe any relevant preliminary data:*

N/A

3.3 *Based on the existing literature, provide the scientific or scholarly rationale for and significance of your research and how will it add to existing knowledge:*

Maintaining adequate energy intake is essential for athletic performance and general health. Yet, many athletes experience low energy availability (LEA) by failing to consume enough calories to meet their energy demands. Recent studies estimate that the prevalence of LEA in athletes ranges from 22% to 58% with a high prevalence in women and endurance sports (Logue, Madigan et al. 2020). Chronic LEA is associated with several inter-related health consequences involving endocrine function, reproduction, and bone metabolism. Impaired bone health is one of the most concerning consequences of chronic energy restriction. Left untreated, prolonged energy deficiency may impair bone accrual during

adolescence and bone formation in adulthood, leading to an elevated risk of fracture and osteoporosis later in life (Papageorgiou, Dolan et al. 2018).

The recommended treatment for LEA is to increase energy availability to optimal levels (45 kcal/kgFFM/d) by increasing EI, decreasing EEE, or a combination of the two (Kuikman, Mountjoy et al. 2021). However, inadequate energy is not always intentional as in the cases of disordered eating/eating disorders and “cutting weight”. Some athletes may experience LEA unintentionally due to factors such as inadequate knowledge of fueling recommendations, decreased appetite, lack of time, or low food security (Wasserfurth, Palmowski et al. 2020). Therefore, not all athletes may be willing or able to achieve optimal energy availability. Given the significant risk to long-term bone health, strategies to counteract the effects of LEA on bone metabolism are necessary.

Compared to inactive controls, runners on average have higher BMD and bone strength (Scofield, Hecht et al. 2012). However, lower total and site-specific BMD has been reported in female endurance runners compared to sprinters and athletes competing in higher impact sports (Tenforde, Carlson et al. 2018, Mudd, Fornetti et al. 2007). Lower BMD in this population may partially be attributed to a high prevalence of LEA and risk of disordered eating (DE) and clinical eating disorders (EDs) among female and endurance athletes (Melin, Tornberg et al. 2015). Mechanical loading through weight-bearing exercises, such as high-impact loading activities and resistance training, provides an osteogenic stimulus and non-pharmacological approach to improving bone health (Hart, Nimphius et al. 2017, Beck, Daly et al. 2017). In a cross-sectional study of male distance runners, BMD was found to be significantly higher in runners who reported routine engagement in resistance training compared to runners who did not weight train and untrained controls (Duplanty, Levitt et al. 2018).

Despite the advantages of resistance training on bone health, recommending additional resistance training to athletes with LEA may further exacerbate energy deficiency if EI is not increased. Thus, physical activity interventions to counteract LEA must be designed to achieve maximal osteogenic responses with the minimal possible energy cost. Adding additional exercise without EI compensation may worsen the state of energy deficiency can cause further damage to the athlete’s health. Even if an athlete does increase EI, adherence to additional routine resistance training is another potential issue. A survey of 667 competitive distance runners found only 60% of respondents engaged in routine resistance training, with middle-distance (800-3,000 m) runners reporting higher participation in strength and conditioning activities compared to long-distance (5k to half-marathon) runners (Blagrove, Brown et al. 2020). Middle-distance runners were 2.7 and 6.7 times more likely to engage in resistance training compared to long-distance and ultra-distance runners, respectively. An alternative to approach to resistance training that would

also apply mechanical loading to the bone is high-impact loading exercises like jumping and plyometric training. Brief jumping exercises have the potential to cause a significant osteogenic bone response with very little energy expenditure, given that a relatively low volume of 10-50 impacts/day at a frequency of 4-7 days/week is required to produce osteogenic effects in premenopausal women (Kishimoto, Lynch et al. 2012, Bailey and Brook-Wavell et al. 2010). The protocol in this proposed study will use jumping exercises at a volume of 5 sets of 10 jumps each day (50 jumps/day) with a 60 second rest between each set. Jumps will be at an intensity of 2x body weight and performed on 5 consecutive days. This approach has several benefits for runners with LEA, with the first being a relatively low energy cost of the jumping intervention which will prevent worsening the LEA state. The second benefit is the short time commitment required for high-impact loading exercises. Given the high running volume of most long-distance runners, engagement in additional cross-training such as resistance exercises may be a challenge. Thus, athletes may find it easier to adherence to the jumping exercises proposed in this study compared to other exercise interventions that require more time and effort. Based on the elevated risk of LEA and low BMD in female endurance runners, this population would benefit from this proposed study.

Findings from this proposed study will be of interest to sports dietitians and athletic trainers based on its potential to improve the clinical management of bone loss in female athletes with LEA through the use of brief, high-impact loading exercises. Future trials based on findings of the proposed study will likely explore the long-term efficacy of high-impact loading during prolonged LEA in active individuals across the spectrum of physical activity levels.

4.0 Study Endpoints

4.1 *Describe the primary and secondary **study** endpoints. See links below for discussion of study endpoints and how they may differ from study objectives. These are most common in clinical trials but are sometimes applicable to other types of biomedical research, as well as social, behavioral, or educational research. See link below for a discussion.*

https://docs.google.com/document/d/1Wocz7K7a0hCQJPPO_khh5l1SQQjhGDDGHzcOPRHR5Tw/edit?usp=sharing

Primary Endpoints

Change in Biomarkers of Bone Remodeling in Blood including N-terminal propeptide of type 1 procollagen, undercarboxylated osteocalcin, sclerostin, and C-terminal telopeptide of type 1 collagen.

22-168 The Effect of Impact Loading on Bone Biomarkers in Energy-Restricted Female Runners

Change in Hormone and Metabolic Markers in Blood including parathyroid hormone, estrogen, insulin-like growth factor 1, hepcidin, insulin, cortisol, leptin, Nesfatin-1, and thyroid hormones

24-h Glucose

Secondary Endpoints

Change in Running Economy

Change in Body Weight

Change in ferritin, TIBC, iron, vitamin D

4.2 *Describe any primary or secondary safety endpoints. These should be included for all studies that are greater than minimal risk. (Minimal risk: The probability and magnitude of harm or discomfort anticipated in the research that are not greater in and of themselves than those ordinarily encountered in daily life or during the performance of routine physical or psychological examinations or tests.):*

Safety Endpoints

Excess weight loss (>5 lbs. during the 5-day experimental conditions)

Excessive change in absolute value for 24-hour glucose concentration

Excessive muscle soreness and/or pain

Fainting or light-headedness

Muscle or joint injury

General fatigue

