5.0 Study Design and Statistical Analysis Plan

5.1 *Describe the basic study design/approach (e.g., qualitative study using five focus groups of first year students to describe assimilation into the university community; randomized controlled trial of a behavioral change intervention to increase dietary intake of whole grains; pre- post-test evaluation of new pedagogical techniques to improve adult literacy):*

This study is a randomized, cross-over intervention study that will evaluate the effect of brief, high-impact loading exercises on biomarkers of bone metabolism in energy-restricted, eumenorrheic female runners. Volunteers will complete two, 5-day experimental conditions in a randomized order separated by one menstrual cycle (approximately 3 weeks). Experimental conditions will include a dietary intervention of energy intake equal to 30 kcal/kgFFM/d using controlled diets and an exercise intervention of daily treadmill running with or without an additional 50 impact loading exercises.

5.2 Describe corresponding data analysis plan/approach (e.g., content analysis of focus group transcripts; descriptive analysis followed by linear regression modeling; nonparametric analysis of pre- and post-test measures):

Data will be analyzed using IBM SPSS statistics software. Paired t-test will be used to detect differences in bone biomarkers and hormones within and between experimental conditions (Aim 1). Associations between undercarboxylated osteocalcin concentration and glucose metabolism (i.e., interstitial glucose concentration and serum insulin) will be analyzed using regression analysis (Aim 2). Data will be summarized as mean \pm 1 standard deviation. The significance level will be set a priori at $p < 0.05$.

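### P1NP is the only marker with a power calculation but is never named as lead: 14 to 16 variables are equally primary, and most are t-tested at an unadjusted 0.05

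*Combined protocol and SAP*

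**What the plan says.** Section 4.1 puts three groups under primary endpoints and does not rank them:

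- bone markers: "Change in Biomarkers of Bone Remodeling in Blood including N-terminal propeptide of type 1 procollagen, undercarboxylated osteocalcin, sclerostin", and CTX;
- hormones and metabolism: "Change in Hormone and Metabolic Markers in Blood including parathyroid hormone, estrogen, insulin-like growth factor 1, hepcidin, insulin, cortisol, leptin, Nesfatin-1, and thyroid hormones";
- the glucose measure, taken over 24 hours.

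Section 5.2 then states: "Paired t-test will be used to detect differences in bone biomarkers and hormones within and between experimental conditions (Aim 1"). A second sentence covers the glucose aim: "Associations between undercarboxylated osteocalcin concentration and glucose metabolism (i.e., interstitial glucose concentration and serum insulin) will be analyzed using regression analysis (Aim 2"). There is one error statement, "The significance level will be set a priori at" p < 0.05. The documents give no hierarchy and no adjustment for multiple tests.

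Three other places bear on which marker leads. The primary objective in 1.0 is broad: "Determine the effect of short-term, high-impact loading on biomarkers of bone remodeling in trained, female long-distance runners" in low energy availability. The only hypothesis, in 2.2, is narrower: less suppression of bone formation with jumping than without. Section 14.1 sizes the trial on a 10 µg/L change in P1NP and on nothing else.

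The status of glucose is inconsistent. It is primary in 4.1. In 1.0 it falls in the row for secondary objectives, worded as "Exploratory Aim: Examine the relationship between undercarboxylated osteocalcin and impact loading on glucose metabolism during acute low energy availability". In 12.2 glucose metabolism is called a secondary outcome.

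**The concern.** The hypothesis and the sample size both point to P1NP, but 4.1 gives it the same standing as every other primary variable. Nothing in the plan says which test decides Aim 1. Under 4.1 and 5.2 as written, a significant difference in CTX, unOC or sclerostin could be reported as a positive primary result even if P1NP showed nothing. The error rate of that claim is not 5%.

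A mixed result is foreseeable from the protocol's own background (3.1). In the cited two-week jumping study CTX fell from baseline, a formation marker also fell, and osteocalcin did not change.

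The within-condition tests open a second route to a wrong conclusion. A significant fall in RUN beside a non-significant fall in RUN+IL is easily read as protection by jumping, but that pattern does not test the difference between conditions.

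**Working it through.** **1. The plan's own figure.** Section 14.1 gives n = 12, a 10 µg/L change in P1NP, 80% power and P < 0.05. It gives no SD, so n = 12 cannot be reproduced. Solving the noncentral paired t backwards (two-sided, n = 12) gives a standardised difference of 0.889, so the implied SD of the difference is 10 / 0.889 = 11.25, about 11.3 µg/L. A one-sided test would imply about 13.0. The documents do not state sidedness; two-sided is assumed below.

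**2. Number of tests.**
- Bone markers: 4 (P1NP, unOC, sclerostin, CTX).
- Named hormone and metabolic markers: 8 (PTH, estrogen, IGF-1, hepcidin, insulin, cortisol, leptin, Nesfatin-1).
- Thyroid hormones: 1 item in 4.1, or the 3 assays in Table 1 (free T3, free T4, rT3).
- Blood markers: 4 + 8 + 1 = 13, or 4 + 8 + 3 = 15. Adding 24-h glucose gives 14 or 16 listed as primary.
- Section 5.2 sends insulin to the Aim 2 regression without saying whether it is also t-tested. Without it the counts are 12 or 14, so the t-tested primary list is 12 to 15 variables.

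**3. At least one false positive, between-condition tests only, all nulls true.** For k independent tests the chance is 1 − 0.95^k:
- k = 1: 5%
- k = 4: 1 − 0.95^4 = 18.5%
- k = 12: 1 − 0.95^12 = 46.0%
- k = 15: 1 − 0.95^15 = 53.7%

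For correlated markers, equicorrelated paired t-tests were simulated (100,000 trials, two-sided 0.05). Every correlation is an assumption.

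| Correlation | 4 bone markers, n = 12 | 4 bone markers, n = 20 | 12 to 15 tests (both n) |
|---|---|---|---|
| 0.3 | 17.7% | 17.5% | 40% to 47% |
| 0.5 | 15.9% | 15.8% | 33% to 38% |
| 0.7 | 13.6% | 13.3% | 24% to 28% |
| 0.9 | 9.7% | 9.6% | 14% to 15% |

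From correlation 0.7 to 0, the four-marker error is 0.133 / 0.05 = 2.7 to 0.185 / 0.05 = 3.7 times nominal. Across the full t-tested list the expected number of false positives is 12 × 0.05 = 0.60 to 15 × 0.05 = 0.75, whatever the correlation.

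**4. Comparing within-condition significance.** Suppose P1NP truly falls by the same amount in both conditions and each within-condition test has 80% power (both assumed). If the two changes are independent, RUN is significant and RUN+IL is not with probability 0.80 × 0.20 = 16%. Simulation (50,000 trials) at correlations 0, 0.5 and 0.7 gives 16.3%, 11.9% and 9.5% at n = 12, and 15.7%, 11.7% and 9.0% at n = 20. The direct between-condition test errs in about 5%.

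**5. Error under the proposed fix.** If P1NP is tested at 0.05 and the other three bone markers by Holm without a gate, the error under independence is 1 − 0.95 × (1 − 0.05/3)^3 = 9.7%. At correlation 0.7 it is 7.7% (n = 12) or 7.5% (n = 20). With the three markers gated on P1NP, it is 5%.

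**6. Alternative: Bonferroni over the four bone markers,** 0.05 / 4 = 0.0125 each. With the back-solved SD of about 11.3, P1NP power at 0.0125 is about 56%, 75% and 87% at n = 12, 16 and 20, against 80%, 91% and 96% at 0.05.

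**The case against.** The 13% to 18.5% depends on a decision rule the plan never states, namely that any one marker suffices. The hypothesis is single, directional and about formation. The protocol describes CTX as a resorption marker and links unOC to resorption, so a chance result on either would not confirm 2.2. P1NP is the evident lead, its test is valid as planned, and in a short biomarker study of 12 to 20 women the gap may be no more than an unwritten label. That would carry the point if the primary objective were limited to formation. It covers bone remodeling, and 4.1 lists all four markers as primary, so a claim on CTX or unOC would be consistent with the text.

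Several parts of the objection stand:

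- The error falls as correlation rises. At 0.9 it is about 10%, still twice nominal. The 46% to 54% for the full list requires independence among markers taken from the same blood draws.
- The 9% to 16% in step 4 is a separate matter and rests on assumed equal falls and assumed power. Section 5.2 does already include between-condition tests.
- The glucose conflict is one of labelling. Glucose goes to regression, so it does not enter the four-marker figure.
- Adjusting across four co-primary bone markers is a legitimate alternative, because the cited jumping evidence concerns resorption as well as formation.
- Section 14.1 does not say that its 10 µg/L is the RUN+IL minus RUN difference. The power of that contrast is therefore unverified.

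**Conclusion.** The concern holds. The plan gives 14 to 16 variables equal primary status, t-tests 12 to 15 of them at an unadjusted 0.05, and does not say which test decides Aim 1. For the four bone markers that match the primary objective, the chance of a false-positive between-condition result is 18.5% under independence and about 13% at correlation 0.7, against 5% for P1NP alone. This assumes all nulls are true, two-sided tests, a common correlation, and that significance on any one marker could be claimed. The count of endpoints and the absence of a rule come directly from 4.1 and 5.2 and need no assumption. This should be corrected, because once results by condition are known the choice of lead marker can no longer be shown to be independent of them.

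**What to change.** In 4.1, name one primary endpoint: the RUN+IL minus RUN difference in Day 1 to Day 7 change in P1NP, tested two-sided at 0.05. Make CTX, unOC and sclerostin secondary, tested by Holm only if P1NP is significant and otherwise reported as estimates with 95% confidence intervals. Move the hormones and 24-h glucose to secondary or exploratory, also as estimates with intervals; for glucose this ends the conflict with 1.0 and 12.2. In 5.2, state that within-condition tests are descriptive and that any claim about jumping rests on the between-condition contrast. Make the change before marker results by condition are seen.

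The cost is wording in 4.1 and 5.2. No further data are needed and the P1NP test loses no power. The price is that CTX, unOC and sclerostin can support a claim only if P1NP is significant, and the hormone and glucose results are no longer confirmatory. If the investigators regard resorption as equally important, adjusting across the four bone markers also holds the error at 5%, at the loss of P1NP power shown in step 6. Whichever they choose, 14.1 should say whether its 10 µg/L refers to the between-condition contrast.
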